16.2. Routine Reporting

For the purposes of this study, the period of observation of AEs extends from the time of first dose (Day 1) until the final clinic visit (i.e., Day 28 follow-up visit [Visit 4] or, if applicable, Early Termination). During this period, all AEs spontaneously reported by the subject, observed by the clinical staff, or elicited by general questioning will be recorded and reported in the eCRF.

Any AE that remains unresolved as of the last visit, the Investigator will attempt to resolve the event or determine the status of the event.

In the case of AEs deemed related to the Investigational Product, every effort will be made to determine the final outcome.

It is the Investigator's responsibility to ensure subjects experiencing AEs receive appropriate follow-up, treatment where required, and that every action is well documented.

Subjects will be questioned on their health status at the beginning of the study period and before the departure from the clinic site. Open-ended questions will be asked.

Classification will be performed by system organ class and preferred term using the Medical Dictionary for Regulatory Activities (MedDRA), version 21.0 or higher.

In general, AEs occurring secondary to other events (e.g., clinical sequelae or a cascade of events) should be identified by their primary cause. For example, if severe vomiting is known to result in dehydration, it is sufficient to record only vomiting as SAE or AE in the eCRF. However, medically significant AEs occurring secondary to an initiating event that are separated in time should be recorded as independent events on the eCRF.

Pregnancy in a female subject on the study shall be reported to the Sponsor's designee within 24 hours of the knowledge of its occurrence by the Principal Investigator or designee (for pregnancies occurring during the course of the study). Because of the possibility that the fetus/embryo could have been exposed to the study drug through the parent and for the subject's safety, the pregnancy will be followed up to determine its outcome, including spontaneous or voluntary termination, details of birth, presence or absence of any birth defects, congenital anomalies, or maternal and/or newborn complications.

The pregnancy will be recorded and reported by the Principal Investigator or designee to the Sponsor's designee. Pregnancy follow-up will also be properly recorded to ensure quality and completeness of the data belonging to the study drug and will include an assessment of the possible causal relation between the study drug and any pregnancy outcome. Any pregnancy will be reported on a Pregnancy Report Form.

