The total duration of study participation will be approximately 4 weeks, including Screening and Follow-up. Study drug treatment will be administered for 14 days.

Safety Assessments:

Adverse Events:

Adverse events will be captured from the time of first dose (Day 1) until the final clinic visit (i.e., Day 28 follow-up visit [Visit 4] or, if applicable, Early Termination (ET) Visit).

Pregnancy Test:

A urine pregnancy test will be performed at Day 1 (Visit 1, Screening/Baseline visit, -3 to 0 days) and at Days 14 (Visit 3) and 28 (Visit 4) for females of childbearing potential. A positive pregnancy test will automatically disqualify the subject from further participation in the trial.

Serum Chemistries, Hematology and Urinalysis:

Blood will be collected for serum chemistries and hematology and urine will be collected for urinalysis at the Screening/Baseline visit, (Day 1, -3 to 0 days) and at the EOT/ET visit (Visit 3, Day 14). A blood sample will be collected at baseline for DNA genotype testing for CYP450 2D6 polymorphism. Subjects will not be informed of the results of the genotype

testing since it is solely for research purposes to determine the phenotype of the enzymes responsible for metabolism of tolperisone. No other DNA testing will be performed.

Vital Signs:

Vital signs, including supine and standing blood pressure, sitting heart rate (after approximately 3 minutes at rest), respiratory rate, and body temperature will be collected at Screening/Baseline (Day 1, -3 to 0 days), and at Days 4, 14, and 28 (All Visits). Weight and height will be measured at Screening/Baseline (Visit 1, Day 1, -3 to 0 days) only.

Electrocardiogram:

Twelve-lead ECG recording will be collected at Screening/Baseline (Day 1, -3 to 0 days) and EOT/ET (Visit 3, Day 14).

Statistical Plan and Methods:

Sample Size:

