9.3. Withdrawal Criteria

Subjects will be advised that they are free to withdraw from the study at any time. Reasons that subjects may discontinue or be withdrawn from the study may include, but are not limited to:

- AEs
- Subject request
- Investigator decision
- Protocol non-compliance
- Study termination by the Sponsor or Institutional Review Board (IRB).

If a subject is withdrawn from the study, all efforts will be made to complete the Visit 3 (EOT) procedures at an Early Termination visit (see [Section 11.2.4](#)). All information, including the reason for withdrawal, should be reported on the applicable pages of the electronic case report form (eCRF).

For subjects who are lost to follow-up, three documented attempts will be made to contact the subject for follow-up information, including reason for discontinuation and follow-up of AEs. Subjects who withdraw from the study will not be replaced.

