10. STUDY DESIGN

10.1. Summary of Study Design

This is a double-blind, randomized, placebo-controlled, parallel group study of the efficacy and safety of multiple doses of tolperisone administered TID in approximately 400 male and female subjects experiencing back pain due to or associated with muscle spasm. The tolperisone groups consist of dose levels of 150, 300, 450, and 600 mg administered TID in doses of 50, 100, 150, or 200 mg for 14 days, with a visit at 28 days as follow-up. Subjects randomized to the placebo group will receive matching placebo tablets TID for 14 days. Subject participation will be approximately 4 weeks.

Subjects will be screened for eligibility for participation in the study at Screening/Baseline Visit 1 (Day 1) after reviewing and signing the informed consent form. Subjects meeting all inclusion/exclusion criteria will then be randomized into the study (Day 1) and begin dosing this same day. If needed, screening assessments may be completed up to 3 days prior to Day 1 (first dose) as described below.

It is highly recommended to complete all screening and baseline assessments on the same day the subject presents at the site due to their acute pain relief needs. However, to accommodate real world logistical issues and time constraints of either the subject or site, the site has the flexibility to allow completion of screening assessments within 3 days (-3 days) prior to Day 1 baseline assessments, deployment of study-provisioned smartphone/download of trial application on subject's smartphone, randomization, and first dose (in that order).

After completing all screening and baseline assessments by/on Day 1, subjects will receive all study drug and rescue medication (acetaminophen 500 mg) and will be instructed to begin taking their study drug that same day. Depending on the time of their clinic visit, they should be instructed to begin dosing with either the midday dose (12-2 pm) or the evening dose (6-8 pm). Subjects will be instructed to continue taking study drug TID through Day 14 and complete dosing diary and daily ePRO assessments.

Subjects will return to the clinic to complete the procedures listed in the Schedule of Procedures on Day 4 (± 1 day; Visit 2) and Day 14 (+1 day, End of Treatment [EOT] visit, Visit 3). Subjects must also return to the clinic for a follow-up visit on Day 28 (+3 days, 2-week follow-up visit, Visit 4).

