11.2.3. Clinic Visit 2: Day 4 (± 1 Day)

On Day 4, subjects return to the clinic to undergo the following assessments:

- Alcohol breathalyzer and urine drug screen. A positive test result for urine drug or alcohol breathalyzer at any time during the study will terminate the subject from further participation in the study.
- Abbreviated physical examination
- Neurological examination
- Vital signs
- Document AEs
- Subject rating of pain (NRS) “right now” via the site study-provisioned tablet
- Subject rating of medication helpfulness via the site study-provisioned tablet
- Global clinical impression of improvement by the physician (CGI-C) via the site study provisioned tablet

- Global impression of improvement by the subject (PGI-C) via the site study-provisioned tablet
- Functionality assessment:
 - Fingers to Floor Distance (FFD)
- VAS via the site study-provisioned tablet
- Disability assessment at Day 4:
 - Oswestry Disability Index (ODI) via the site study provisioned tablet
- For the select group of sites and subjects who will undergo PK assessments, a single blood sample will be drawn on Day 4 after all other assessments have been completed.
- Any changes or additions to prior concurrent medication use will be recorded. Confirm that no rescue medications were taken on Day 4 (Visit 2).
- Site staff to review returned study drug and rescue medication against the eDiary dosing information to evaluate compliance.

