15. DISCONTINUATION CRITERIA AND PROCEDURES

According to the Declaration of Helsinki, all subjects have the right to withdraw from a study at any time, regardless of their reasons. In addition, it is the right of the Investigator to remove subjects from the study as a result of AEs, protocol violation, or any other reason.

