7.5.1 *Extent of Exposure*

Extent of exposure to study treatment will be summarized for the Safety Population by treatment group. The date of first and last dose is collected on the eCRF. If missing, subjects’ dosing eDiary data will be used to determine dates of first and last doses. The duration of exposure will be presented in days and calculated as the date of last dose of study drug minus the date of first dose of study drug, plus one. Duration of exposure, average dose received, and total dose received (mg) will be summarized using descriptive statistics.

Total dose received will be derived based on the number of tablets returned at the end of treatment visit and the actual dose (mg) received. Average dose will be calculated as the total

dose divided by the duration of exposure. The planned number of doses for each subject is 42 (14 days of TID dosing).

7.5.2 *Adverse Events*

Treatment-emergent adverse events (TEAEs) are defined as those adverse events (AEs) with onset on or after the first dose of study drug through 24 hours after the last dose of study drug. Existing events that worsened during this period will also be considered treatment emergent. If start time is not available, AEs with onset between the date of the first dose through the day after the date of last dose (+1 day) will be considered treatment-emergent.

Adverse events with onset greater than 24 hours (or >1 day) after the date of the last dose of study drug through the date of the follow-up visit (Visit 4/Day 28) will be considered after-treatment events.

Treatment-emergent and after-treatment AEs will be summarized by treatment group. Events reported with a partial onset date (e.g., month and year are reported but the day is missing) will be considered to be treatment-emergent if it cannot be confirmed that the event onset was prior to the first dose of study drug based on the available date entries.

Verbatim terms on case report forms will be mapped to preferred terms and system organ classes using the Medical Dictionary for Regulatory Activities (MedDRA, version 21.1).

Summaries that are displayed by system organ class and preferred terms will be ordered by descending incidence of system organ class and preferred term within each system organ class. Summaries displayed by preferred term only will be ordered by descending incidence of preferred term. Summaries of the following types will be presented:

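### Adverse event collection stops at the Early Termination visit, so new events after it are not sought in early leavers and after-treatment AE incidence is under-counted

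*Protocol*

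**What the plan says.** **End of AE observation.** Protocol 16.2 observes AEs from first dose "until the final clinic visit (i.e., Day 28 follow-up visit [Visit 4] or, if applicable, Early Termination". The Safety Assessments part of the synopsis gives the same rule: "until the final clinic visit (i.e., Day 28 follow-up visit [Visit 4] or, if applicable, Early Termination (ET) Visit".

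**What an early leaver gets.** Under Protocol 9.3, "all efforts will be made to complete the Visit 3 (EOT) procedures at an Early Termination visit"; Protocol 11.2.4 repeats this. Neither section assigns that subject Visit 4 or any later contact.

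**What a completer gets.** Protocol 10.1: "Subjects must also return to the clinic for a follow-up visit on Day 28 (+3 days, 2-week follow-up visit, Visit 4". Protocol 11.2.5 lists AE recording, vital signs, an abbreviated physical examination and a pregnancy test at that visit.

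**Who leaves early.** AEs head the list of withdrawal reasons in Protocol 9.3, and Section 15 says "it is the right of the Investigator to remove subjects from the study as a result of AEs, protocol violation, or any other reason". Protocol 11.2.3 adds: "A positive test result for urine drug or alcohol breathalyzer at any time during the study will terminate the subject from further participation". Protocol 11.2.4 repeats that screen at Visit 3. Protocol 12.17 applies the same consequence to a positive pregnancy test.

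**What remains covered.** For an AE unresolved at the last visit, Protocol 16.2 says that "the Investigator will attempt to resolve the event or determine the status of the event"; it also seeks the outcome of related AEs and follows pregnancies to outcome. Protocol 16.3 requires SAE notification within 24 hours of awareness and states no end date. Protocol 9.3 provides three contact attempts for subjects lost to follow-up. SAP 7.5.3 lists all deaths, including those in post-treatment follow-up.

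**Analysis.** SAP 7.5.2 ends the TEAE window 24 hours after the last dose. Later events "through the date of the follow-up visit (Visit 4/Day 28) will be considered after-treatment events", and they are summarised in one incidence table by preferred term. SAP 7.5 includes a non-completer's data up to termination.

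**The concern.** Follow-up for new events is shortest in a group that includes subjects withdrawn because of an AE. A completer has about two weeks of off-drug observation, and an early leaver has none planned beyond the Early Termination visit. Read literally, a subject who took every dose could also lose Visit 4 because of a drug or alcohol test taken at Visit 3.

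The SAP then tabulates after-treatment AEs through Day 28 without saying who was under observation for them. If more subjects leave early at the higher doses, those arms could look safer in that table than they are. Safety and tolerability is a secondary objective, and the synopsis says the study is meant to identify the Phase 3 dose.

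**Working it through.** The documents state no late-AE rate and no early-termination rate by arm, so there is no plan figure to reproduce. The check has a text part and an illustration.

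**1. Length of observation.** With the last dose on Day 14, Visit 4 on Day 28 falls 28 − 14 = 14 days later, and on Day 31 it falls 31 − 14 = 17 days later. For an early leaver, planned observation for new events ends at the Early Termination visit.

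**2. Which events are missed.** Compare the rule with the safeguards:
- An AE open at the last visit, or judged related: followed up.
- Pregnancy: followed to outcome.
- Death, or an SAE the site learns of: reportable, or listed.
- A new non-serious AE after Early Termination: outside the observation period, with no contact planned.
- A new SAE after Early Termination that nobody reports: no planned contact would bring it to light.

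**3. Which outputs are touched.** The SAP's TEAE window closes 24 hours after last dose for every subject, so those tables depend little on Visit 4. An exception is an Early Termination visit less than 24 hours after the last dose. The summary that uses the later period is the after-treatment AE table.

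**4. Illustrative size (all rates assumed).** Let r be the completers' after-treatment AE risk, d the share terminating early, and m the leavers' risk relative to completers. Assume that nothing is observed in leavers after treatment.

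- Collected proportion, full-arm denominator: r(1 − d)
- Proportion under full follow-up: r(1 − d) + m·r·d
- Shortfall in one arm: m·r·d
- Distortion of the active-minus-placebo difference, with r and m equal across arms: −m·r·(d_active − d_placebo)

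| Early termination, active vs placebo | r | m = 1 | m = 3 |
|---|---|---|---|
| 5% vs 5% | 2%, 5% or 10% | 0 | 0 |
| 15% vs 5% | 2% | −0.2 points | −0.6 points |
| 15% vs 5% | 5% | −0.5 points | −1.5 points |
| 15% vs 5% | 10% | −1.0 point | −3.0 points |
| 30% vs 5% (extreme) | 5% | −1.25 points | −3.75 points |
| 30% vs 5% (extreme) | 10% | −2.5 points | −7.5 points |

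Example: 3 × 0.10 × (0.15 − 0.05) = 0.030, or 0.030 × 80 = 2.4 subjects in an arm of 80. Even with equal early termination, each arm loses m·r·d; the two losses simply cancel in the difference.

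**5. Same illustration, denominator restricted to subjects observed.** The collected proportion is r(1 − d)/(1 − d) = r in both arms. The distortion becomes −(m − 1)·r·(d_active − d_placebo). At 15% versus 5% and r = 10%, this is 0 for m = 1 and −2 × 0.10 × 0.10 = −2.0 points for m = 3. A better denominator removes the part due to missing person-time. It cannot recover the excess risk in leavers; only follow-up can.

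**The case against.** The strongest reply is that this is a consistent design choice with narrow consequences. The synopsis and Protocol 16.2 agree, the main safety tables are fixed to a 24-hour window, and serious outcomes have their own reporting routes. All of that stands, and it limits the point to new events after Early Termination and chiefly to one descriptive table. It does not show that anyone looks for those events.

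A reader might infer more than the documents support:

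- **That late AE rates are biased between arms.** This needs early termination, or leavers' late risk, to differ by arm. No such rates are given. Protocol 7.3.2 reports no increase in AEs in an earlier study at up to 900 mg/day. The 5% and 15% dropout figures in SAP 7.4.6.2 trigger imputation of efficacy data and are not forecasts.
- **That the direction of the comparison reverses.** Assume 3/80 leave early on placebo and 12/80 at 600 mg, with risks of 10% in completers and 30% in leavers. Full follow-up gives (7.7 + 0.9)/80 = 10.75% and (6.8 + 3.6)/80 = 13.0%. Collected over 80, the figures are 7.7/80 = 9.6% and 6.8/80 = 8.5%. SAP 7.1.1, however, sets subjects with available data as the default denominator. On that basis the figures are 7.7/77 and 6.8/68, both 10.0%, and the reversal disappears, although the real excess is still hidden.
- **That the SAP counts every early leaver as event-free.** SAP 7.5.2 names no denominator, and it is unclear how the default in 7.1.1 applies to AE tables. The fault is silence.
- **That late events in AE dropouts are never recorded.** Protocol 16.2 and 16.3 and SAP 7.5.3 still reach open and related AEs, pregnancies, notified SAEs and deaths.
- **That stopping drug always means leaving the study.** Protocol 9.3 lists reasons why subjects may leave, Protocol 10.2.1 allows temporary discontinuation, and the SAP separates study discontinuation from drug discontinuation. The gap concerns those who leave the study.

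**Conclusion.** The point holds in a limited form. By stated rule, early leavers have no planned ascertainment of new-onset events after the Early Termination visit, while completers have about 14 to 17 days after Day 14. After-treatment AE incidence is therefore under-counted in early leavers.

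Bias between arms is possible but not shown. On assumed rates it is nil when early termination and late risk are alike, and 0.2 to 3.0 points at 15% versus 5% on a full-arm denominator. If an Early Termination visit takes place some days after the last dose, part of the off-drug period is observed and the loss is smaller.

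The conclusion that the TEAE tables are largely unaffected rests on the SAP's 24-hour window. The TEAE definition in Protocol 16.1 has no end, and SAP 7.7.1 does not list the cut-off as a change. If the open-ended definition were used, the effect would reach those tables too. The SAE incidence table in SAP 7.5.2 states no window, so its exposure to the gap cannot be judged.

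**What to change.** **Protocol.** In the synopsis and 16.2, collect AEs for every dosed subject through one stated off-drug window of the same length for all, by clinic visit or by telephone, unless consent is withdrawn. At least 14 days after the last dose is one example; Visit 4 already meets it for a subject whose last dose is on Day 14. Name a single end point: for a subject who stops on Day 3, 14 days after the last dose is Day 17, not Day 28. In 9.3, 11.2.3, 11.2.4 and 12.17, state that leaving the study early does not end this AE collection. The termination rules themselves need not change.

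**SAP 7.5.2.** Use the subjects actually observed after treatment as the denominator for after-treatment AEs, and report post-treatment follow-up time by arm. This part can be done even if enrolment is complete. That matters because SAP 7.7.2 describes a May 2019 audit of trial conduct, and a protocol change cannot recover events in subjects who have already left.

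**Cost.** A short amendment, a few lines in the SAP, and one extra contact for the minority who leave early, some of whom will not respond. Sample size and significance level are unchanged.

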16.3. Serious Adverse Event Reporting

The sites will notify the sponsor and sponsor's designee of any SAE, without regard to causality, within 24 hours after becoming aware of its occurrence.

If, during follow-up, any non-serious AE worsens and eventually meets the criteria for an SAE, that AE should be recorded as a new SAE.

The initial SAE report must be as complete as possible, including details of the current illness and SAE, and an assessment of the causal relationship between the event and the investigational product(s). Information not available at the time of the initial report (e.g., an end date for the AE, laboratory values received after the report, or hospital discharge summary) must be documented. All follow-up information must be reported as soon as the relevant information is available.

The SAE notification should be reported by completing the SAE report form in the EDC.

An SAE will be considered "unexpected" if the AE is not listed in the Investigator's Brochure or is not listed at the specificity or severity that has been observed; or, if an Investigator's Brochure is not required or available, is not consistent with the risk information described in the General Investigational Plan or elsewhere in the current application. "Unexpected," as used in this definition, also refers to AEs that are mentioned in the Investigator's Brochure as occurring with a class of drugs or as anticipated from the pharmacological properties of the drug, but are not specifically mentioned as occurring with the particular drug under investigation.

The sites will determine whether any serious unexpected related AE must be reported to the IRB. If so, the event will be reported via fax or email or as required per IRB once the Investigator or staff becomes aware of the event.

The sponsor will determine whether the SAE must be reported in an expedited manner to the appropriate regulatory agencies. If so, the Sponsor will report the event to the appropriate regulatory agencies, and all participating Investigators.

If reports of any new and unexpected AEs become available to the Sponsor during the clinical portion of this study (related or not to the present study), the Sponsor must advise the sites of those events.

